### Evaluation Metrics

Domain	Metric	Target
Recruitment	• Screening rate	70%
Feasibility	• Eligibility rate	50%
	• Reasons for ineligibility	--
	• Enrollment rate	30%
Acceptability of Procedures	• Baseline questionnaire adherence	75%
	• Post-session survey adherence	60%
	• Post-CALM questionnaire adherence	60%
	• Exit interview adherence	60%
Intervention Acceptability	• Intervention Completion of Trial Initiators	70%
	• Reason for withdrawal	--
	• Intervention satisfaction survey benefit rating	Rating $\geq$ 4/5
	• CEQ rating (preliminary)	$\geq$ 14

### Psychological Distress and Life Quality Outcome Measures

Measure	Items	Distress Descriptors
Patient Health Questionnaire	PHQ-9	9 0-5 5-9 10-14 15-19 20-27 Minimal Mild Moderate Moderately Severe Severe
Death and Dying Distress Scale	DADDS	15 0-24 25-46 47-75 Low Moderate Severe
Generalized Anxiety Disorder	GAD-7	7 0-4 Minimal

			5-9	Mild
			10-14	Moderate
			15-21	Severe
Quality of Life at the End-of-Life Cancer Scale	QUAL-EC	17	0-68	--
Functional Assessment of Chronic Illness Therapy – Spiritual Wellbeing Scale	FACIT-sp	12	0-48	--
Fear of Cancer Recurrence	FCR-7	7	$\geq 17$ $\geq 27$	60 th percentile 90 th percentile
Post-Traumatic Stress Disorder Checklist	PCL-5	20	$\geq 31$	Probable PTSD
Suicidal Ideation	PHQ-9	1	0-3	--
Tobacco, Alcohol, Prescription medication and other Substance Use	TAPS	4	0 1 2	No Use Problem Use Higher Risk

## DATA ANALYSIS.

Detailed records of the number of individuals who screen, are eligible, enroll, complete assessment measures, and attend telehealth sessions will be kept. Reasons for attrition will be recorded. Individuals who “no-show” will be contacted to assess continued interest and will be rescheduled as appropriate. Each attempt to contact participants will be recorded. This information will guide future recruitment/retention and inform feasibility. Recruitment source will be tracked to determine the most fruitful strategies. We will calculate frequencies and proportions to explore preliminary feasibility outcomes and means and standard deviations or medians and interquartile ranges to assess preliminary acceptability. The two-sample t- tests and/or Mann-Whitney U-test, and chi-square tests will be used to compare eligible patients who did and did not enroll in terms of demographic, medical, and psychiatric variables. Within-group changes in behavioral and psychological variables will be explored to prepare for future pilot and efficacy trials. Thus, for each data collection time points we will calculate the mean and standard deviation of exploratory outcomes. In addition, we will calculate the correlation on the measures between time points as well as calculating the difference scores and the accompanying standard deviations.

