**Treatment options for individuals with brain cancer are lacking.** Medical advances have nearly doubled median survival rates over the past decade (28, 29). However, there is still no cure for malignant brain cancer. The median overall survival for patients with bMET is now approximately 6 months, with 1- and 2-year survival rates at 8.3% and 1.4%, respectively (30). Medical interventions targeting amelioration of PBT and bMET are associated with a range of adverse effects, including cognitive decline and fatigue, compounding the symptoms of the disease itself. Given this poor prognosis, medical management often focuses on symptom alleviation (e.g., the provision of steroids to reduce brain swelling, anticonvulsants to reduce seizure frequency) (31). Tailored, evidence-based behavioral health interventions for SMs, Veterans, their beneficiaries, and civilians with brain cancer that focus on preparation for living with a brain tumor, its treatment, and the fatal disease trajectory are not only essential for mission readiness, but are also mission critical.

**Brain cancer is associated with significant distress and reduced quality of life.** In the absence of curative medical treatments for malignant PBT and bMET, care must include a focus on increasing psychological preparedness and improving quality of life. Nearly all patients with PBT (93%-95%) report symptoms of depression (32, 33), with rates of clinical diagnoses greater than both other oncology populations and the general population (22%- 41% v. 13% v. 7%, respectively) (33-38). Our own preliminary data demonstrate that those with PBT endorse a particular type of distress—death anxiety—at a drastically higher rate than other cancer populations (81% v. 32%) (39). Death anxiety refers to fear and preoccupation with thoughts of death and dying that may interfere with individuals' daily functioning. Anxiety regarding death is understandable among those with brain cancer given the uncertain disease trajectory, lack of curative treatment, potential loss of functioning, and the inherent existential nature of brain cancer itself (40). In advanced cancer patients, behavioral health interventions that focus on increasing preparedness, finding meaning, and understanding disease trajectory have been shown to reduce distress, and improve mood and life quality (25).

[figure not shown]

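### Do the exploratory means and change scores need a defined analysis set and a baseline comparison of participants with and without follow-up data?

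*Combined protocol and SAP*

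**What the plan says.** All the relevant text is in the Data Analysis section of the combined protocol and SAP. The purpose is modest: "Within-group changes in behavioral and psychological variables will be explored to prepare for future pilot and efficacy trials". Two sets of summaries serve it. First, "for each data collection time points we will calculate the mean and standard deviation of exploratory outcomes". Second, "we will calculate the correlation on the measures between time points as well as calculating the difference scores and the accompanying standard deviations". No analysis set is named for either.

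On selection, t-tests or Mann-Whitney tests and chi-square tests "will be used to compare eligible patients who did and did not enroll". After enrollment, the section says of attrition: "Reasons for attrition will be recorded". It also says that counts of those who "complete assessment measures, and attend telehealth sessions will be kept". The Aim 1 section adds that people who withdraw are contacted and asked why. No comparison of baseline profile by follow-up status is planned.

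The Evaluation Metrics table sets targets of 75% for the baseline questionnaire, 60% for the post-CALM questionnaire and 70% for completion of the intervention. It lists no target for the 3-month survey. The Significance section gives the background prognosis: "The median overall survival for patients with bMET is now approximately 6 months", with "1- and 2-year survival rates at 8.3% and 1.4%, respectively".

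**The concern.** The last survey comes 3 months after an intervention that itself takes 3 to 6 months, so about 6 to 9 months after CALM starts. Against the quoted survival, substantial loss by then is plausible. If the people who remain were less distressed at the outset, the raw means would fall over time although nobody had improved. The paired difference scores would describe only those who stayed.

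A later team planning a pilot or efficacy trial could take a mean change, its SD and a correlation from this study without knowing whom they represent. Counts and reasons for loss would show how many were lost and why, but not whether they differed at baseline.

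**Working it through.** The text available gives no sample size, expected change or SD, so there is no figure of the plan's own to reproduce. The checks below ask what the plan leaves undetermined and how much could turn on it.

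**1. Which sets are really open?** A difference score and a between-time correlation both need two measurements on the same person, so they are paired by construction. Only the time-point means leave a choice, and the plainest reading is everyone with data at that time.

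**2. How many pairs?** Take the Evaluation Metrics targets as exactly met. Their denominators are not stated, so two readings are shown. The share with both surveys lies between max(0, b + p − 1) and min(b, p), where b is the share of enrolled with a baseline survey and p the share with a post-CALM survey.

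| Reading | b | p | Lowest | If independent | Highest |
|---|---|---|---|---|---|
| 60% is of all enrolled | 0.75 | 0.60 | 0.35 | 0.75 × 0.60 = 0.45 | 0.60 |
| 60% is of completers, 70% completing | 0.75 | 0.70 × 0.60 = 0.42 | 0.17 | 0.75 × 0.42 = 0.315 | 0.42 |

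Post-CALM responders with no baseline survey could be 0% to 0.25/0.60 = 42% in the first reading and 0% to 0.25/0.42 = 60% in the second. Under independence the figure is 25% in both. The targets alone do not settle it.

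**3. How much loss from death?** A Weibull curve through 50% at 6 months and 8.3% at 12 months has shape ln[ln(1/0.083)/ln 2]/ln 2 = 1.84. It gives 23% alive at 9 months. Linear interpolation gives (0.50 + 0.083)/2 = 29%, and log-linear √(0.50 × 0.083) = 20%. These figures cannot carry much weight:

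- The Significance section gives no time origin.
- Participants are selected on cognition and internet access and may live longer.
- The same Weibull gives 0.01% at 24 months against the stated 1.4%.

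**4. How far could a raw mean move?** With complete baseline data and no change in any individual, the shift equals (share lost) × (baseline gap between retained and lost). The gap is not known, so this restates the loss and establishes no size.

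**5. An illustration with every input assumed.** True mean change is zero, 60% respond afterwards, the between-time correlation is 0.5 or 0.7, and the tendency to respond is correlated 0.2 or 0.4 with lower later distress. Results are in SD units.

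| Correlation | Selection | Later mean minus full baseline mean | Paired change | Retained baseline mean | SD of change | Observed correlation |
|---|---|---|---|---|---|---|
| 0.5 | none | 0.001 | 0.001 | 0.001 | 1.000 | 0.500 |
| 0.5 | 0.2 | −0.129 | −0.064 | −0.064 | 0.997 | 0.495 |
| 0.5 | 0.4 | −0.257 | −0.129 | −0.127 | 0.988 | 0.482 |
| 0.7 | none | −0.001 | −0.001 | −0.000 | 0.774 | 0.701 |
| 0.7 | 0.2 | −0.129 | −0.038 | −0.090 | 0.773 | 0.697 |
| 0.7 | 0.4 | −0.259 | −0.077 | −0.183 | 0.769 | 0.683 |

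Three things follow.

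- Paired change is not immune. It moves by 0.04 to 0.13 SD because loss here depends on the later score. It is unbiased only if loss is unrelated to change.
- The SD of change and the correlation, which a later sample-size calculation would use, hardly move. The largest falls are 1.000 to 0.988 and 0.500 to 0.482.
- The planned outputs already expose a shift in who is being described. The later mean minus the mean difference gives the retained group's baseline mean: −0.257 − (−0.129) = −0.128, against −0.127 simulated. This is exact only if every later responder has a baseline score.

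**The case for a change.** The strongest case for a change is that the remedy is cheap and serves the plan's declared purpose. Loss is foreseeable, counts and reasons do not reveal baseline differences, and even the paired change can be biased. Pair counts, a second row of means and one descriptive table by follow-up status would need little beyond what is collected. PHQ-9 and DADDS are used for eligibility, so screening values should be available for many who skipped the baseline survey.

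Much of this stands. The reading of the text is right, and such a table would be good reporting. But it would alter none of the planned estimates and would not correct a bias that depends on unobserved later scores. It would not deal with regression to the mean either, which can arise because enrollment requires an elevated PHQ-9 or DADDS score. Counting deaths separately is free only if the recorded attrition reasons already capture them; otherwise it needs new ascertainment. With small numbers likely, the table could only be descriptive.

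**Conclusion.** No change to the plan is called for. The analysis set for the time-point means is unwritten, but the sensible choice is evident. The change scores and correlations are paired by construction, and the records needed to report numbers and reasons for loss are already planned. No stated rule produces a wrong result.

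The effect on the primary feasibility endpoints is nil. For the exploratory outcomes, the share with baseline-to-post pairs could be anywhere from 17% to 60% of enrolled across the two readings of the targets. That is a reason to print n beside each summary, which analysts would do unprompted. The size and direction of any selection bias cannot be derived from the documents, and the 0.04 to 0.26 SD shifts in paired change and raw means rest entirely on assumed selection.

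This conclusion assumes that the results are used as the plan describes, to explore change in preparation for later trials, and that numbers and attrition are reported with them. It does not assume that paired change would be zero in the absence of benefit.
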